8.1.1. Patient Disposition

All subjects will be accounted for. All early withdrawals will be summarized by primary reason for discontinuation; these will be summarized by treatment group.

Treatment exposure (time in trial and time on treatment) will be summarized by cohort for all subjects in the analysis dataset.

8.1.2. Baseline Characteristics

Demographic (age, sex, ethnicity, and race) and baseline body measurements and vital signs (height, weight, BMI, heart rate, blood pressure, and ECG assessments) will be summarized.

Ordinal Scale for Clinical Improvement (OSCI) score at screening will be summarized.

8.1.3. Medical History

Medical history will be coded in MedDRA and summarized by System Organ Class (SOC) and Preferred Term (PT).

8.1.4. USB002 Administration

USB002 administration data, including dose of administration, infusion start/end date, start/end time, start rate of infusion, and all information of infusion rate changes, infusion incompletion reason, and related AEs, if applicable, will be listed.

8.1.5. RT-PCR SARS-CoV-2 Test

RT-PCR SARS-CoV-2 Test at screening will be listed.

8.2. Primary Outcomes

The primary endpoint of the study will be safety and tolerability, as demonstrated by adverse events (AE), changes in laboratory assessments, ECG assessments, vital signs, and concomitant medications (inotropes and vasopressors). These outcomes will be summarized by cohort. See details in sections 8.2.1 to 8.2.6.

Co-primary endpoint is the difference between USB002 and placebo groups in time to peripheral capillary oxygen saturation (SpO₂) $\geq 94\%$ on room air, sustained for at least 48 hours, through Day 28. All peripheral capillary oxygen saturation (SpO₂) results from baseline to Day 28 will be listed (and summarized if applicable). See section 8.2.7.

No statistical inference will be made for primary endpoint.

8.2.1. Adverse Events

Only treatment emergent adverse events (TEAEs) will be summarized. Summaries will be provided by dose level cohort with all placebo groups combined. Following summaries will be provided:

- Overview of TEAEs - include the total number of TEAEs, serious TEAEs, DLT, and TEAE leading to death
- TEAEs by MedDRA System Organ Class (SOC) and Preferred Term (PT)
- TEAEs by MedDRA SOC, PT, and severity
- TEAEs by MedDRA SOC, PT, and relationship to treatment
- TEAEs by MedDRA SOC, PT, and outcome
- Serious TEAEs by MedDRA SOC, and PT
- TEAE leading to death
- DLT.

All these summaries will include the counts and frequencies of events, and of subjects who had events.

All TEAEs will be listed by subject. Serious TEAEs, TEAEs leading to death, and DLTs will be listed separately.

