If a subject's treatment is terminated after the Visit 1/Day 1 infusion begins, for any reason, all attempts will be made to conduct all remaining study visits and assessments,

as applicable (See Tables 2 and 3). End of Treatment (Part 1 – Visit 5; Part 2 – Day 16) procedures may be conducted during the 24-hour observation period. Missed End of Treatment assessments due to disease progression or early discharge, will be considered deviations.

Respiratory evaluations will be determined by recovery landmarks of time to acceptable spontaneous breathing efforts (up to 30 minutes), termination for the need of oxygen (see Spontaneous Breathing Trial [SBT]: Appendix 2), and time to discontinuation of ventilatory assistance, if applicable. Clinical status will be evaluated using the OSCI and physical examination findings.

Follow-up for AEs with a start prior to Day 28 will be followed to resolution, stabilization, or to Day 60. Survival will be captured during the follow-up period through to Day 60, regardless of treatment or hospitalization status. AEs with a start date after Day 28 will not be captured. Any SAE that occurs at any time, through to Day 60, will be collected.

Participation will terminate for all subjects on Day 60 or at early termination due to death, consent withdrawal or lost to follow-up.

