### **6.4. Reporting Procedures**

#### **6.4.1 Adverse Event Reporting**

AEs will be captured from the start of USB002/placebo infusion until Day 28 or hospital discharge, whichever occurs last. Any AEs ongoing at Day 28 (or discharge) will be followed/assessed up to the Day 60 Telemed visit. No new AEs will be collected following discharge. SAEs (new or ongoing) will be followed and/or collected until Day 60.

All AEs (whether attributable to the study drug) occurring during the study observed by the Investigator or reported by the subject will be recorded on the eCRF. The following information will be recorded for all AEs:

- Event: name/condition/diagnosis/description;
- Onset and resolution time and/or date;
- Severity;
- Relationship to study drug (assessment by staff trained and authorized to

diagnose);

- Action taken;
- Seriousness.

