3.1. Primary Objective

The primary objectives of safety and tolerability of USB002 will be evaluated for rate of occurrence and severity of AEs resulting from clinical changes (Visit 1/Day 1 to Day 28): cardiovascular parameters, to include blood pressure (BP), heart rate (HR), 12-lead electrocardiogram (ECG), and requirements for inotropes and vasopressors; laboratory parameters, to include kidney and liver function.

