7.2. Calculated Outcomes

The following are key endpoints derived from data captured at the sites via the EDC system. Complete documentation of the calculations and data manipulation required to go from the CRF database to the analysis database are contained in the companion documents – SDTM Programming Specification File (SDTM Spec) and ADaM Programming Specification File (ADaM Spec).

Outcome	Calculation	Comment
Study Day	= the days from Day 1 (Date of the First Study Infusion) to the event date	
Time in Trial (days)	= Study completion/withdrawal date – date of informed consent date + 1 day	
Time on Treatment	= Date of last infusion – Date of first infusion + 1	
Baseline value	= Value reported prior to the first study treatment	If multiple values collected prior to the first infusion, non-missing value closest to the date/time of the first infusion is considered as baseline value
Change from Baseline	= Value collected at time point (Visit) – Baseline value	
BMI	= $10000 * (\text{Weight in kg}) / (\text{Height in cm})^2$	Value will be rounded to keep one decimal point
Treatment Emergent Adverse Event (TEAE)	= No, if onset date/time AE is before the date/time of the first study infusion = Yes, otherwise	According to conservative rule, all AEs that cannot be determined as started before the first study infusion will be considered as TEAE

Outcome	Calculation	Comment
Time from baseline to achieving $\text{SpO}_2 \geq 94\%$ on room air	= Date of first achieving $\text{SpO}_2 \geq 94\%$ on room air – Date of first infusion + 1 = null if the subject did not achieve $\text{SpO}_2 \geq 94\%$ till study termination	
Number of ventilator-free days	= the number of days between Day 1 and Day 28 that subjects are both alive and free of mechanical ventilation	
Weaned from MV (Yes/No)	= Yes, if the subject was on MV and then weaned from MV through Day 28 = No, if the subject was on MV and kept using MV till Day 28 = null, if the subject did not use MV from Day 1 to Day 28	
Progressed to MV (Yes/No)	= Yes, if the subject progressed from non-invasive (at baseline) to MV on/before Day 28 = No, if the subject was keeping non-invasive till Day 28	
Time to Progression (TPP)	= First MV date – Date of first infusion + 1 = null, if the subject was keeping non-invasive till Day 28	
Time to hospital discharge	= Hospital discharge date – Study Day 1 + 1 = null if the subject was staying in hospital till Day 28	

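### The primary adverse-event tables have no Day 28 cut-off, so serious events starting on Days 29 to 60 enter them outside the objective's window and without matching capture of non-serious events

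*SAP*

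**What the plan says.** **The objective has a window.** SAP 3.1, repeating protocol 2.1.1, defines the primary safety objective as "rate of occurrence and severity of AEs resulting from clinical changes (Visit 1/Day 1 to Day 28"; the protocol synopsis gives the same period.

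**The flag does not.** In SAP 7.2 an event is not treatment-emergent if it starts before the first infusion, and is treatment-emergent otherwise. The comment adds that "all AEs that cannot be determined as started before the first study infusion will be considered as TEAE". There is a lower bound and no upper one.

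**Nor do the tables.** SAP 8.2.1 summarizes treatment-emergent events only, beginning with "Overview of TEAEs - include the total number of TEAEs, serious TEAEs, DLT, and TEAE leading to death" and continuing by system organ class and preferred term, severity, relationship and outcome, with separate summaries for serious events, deaths and dose-limiting toxicities. Each gives counts of events and of subjects. No onset window is stated.

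**Collection differs by seriousness, and the protocol gives two accounts of it.** Protocol section 3 says "AEs with a start date after Day 28 will not be captured" but also "Any SAE that occurs at any time, through to Day 60, will be collected". Protocol 6.4.1 says "AEs will be captured from the start of USB002/placebo infusion until Day 28 or hospital discharge, whichever occurs last", then "No new AEs will be collected following discharge", and for serious events "SAEs (new or ongoing) will be followed and/or collected until Day 60".

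**The concern.** Take two events that both start on Day 45 in a subject already discharged, one serious and one not. Under either protocol section the serious one is collected and the other is not. The SAP flag then places the serious one in every relevant 8.2.1 table. Those tables are the primary safety result, and their stated purpose is Days 1 to 28.

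Two things follow. The tables report a period longer than the objective without saying so. Within them, serious and non-serious events are also observed for different lengths of time, so the mix of the two partly reflects the collection rules and not only tolerability.

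The setting makes this more than a formality. All 21 enrolled subjects are in Part 1 (SAP section 2), where infusion lasts at most 96 hours. An event on Day 29 begins about 24 days after the latest possible end of infusion (28 days minus 4) and would still be labelled treatment-emergent. Protocol 6.1.1 counts disease progression as an adverse event, so late serious events are plausible. The analysis is descriptive (SAP 7.4), so a reader has the counts and little else.

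**Working it through.** The plan states no figure on this point, so there is nothing to reproduce. The check covers the windows, the effect on incidence, and an illustration under assumed rates.

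**1. Length of capture.** With serious events collected to Day 60, serious-only time is 60 minus the last day of full capture.

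| Case | Section 3 | 6.4.1, later of Day 28 and discharge | 6.4.1, nothing new after discharge |
|---|---|---|---|
| Discharge Day 10 | 28 + 32 | 28 + 32 | 10 + 50 |
| Discharge Day 28 | 28 + 32 | 28 + 32 | 28 + 32 |
| Discharge Day 45 | 28 + 32 | 45 + 15 | 45 + 15 |

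Each cell shows days of full capture plus days of serious-only capture. The switch point moves with the rule, but a serious-only period remains for every subject discharged before Day 60.

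**2. Direction.** Removing the Day 28 limit adds serious events and removes none, so the serious count stays the same or rises under any of these rules. The serious *share* must also stay or rise under section 3, where nothing non-serious is added after Day 28. Under the later-of-two-dates rule this is not guaranteed, because non-serious events after Day 28 are added too for subjects still in hospital.

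**3. Effect on incidence.** One subject whose only serious event is late changes incidence by 100/n percentage points.
- Active cohort with n = 3, the planned number per dose: 100/3 = 33.3 points.
- Pooled placebo: three per completed cohort gives 9, plus 0 to 3 from the three subjects in Cohort 4, whose split is not given. So n is 9 to 12, and the change is 11.1 to 8.3 points.

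**4. Illustration for the serious share (section 3 rule; all rates assumed).** Let s be the serious share of events by Day 28, and r the daily serious-event rate after Day 28 divided by the rate before it. Then

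share = s(1 + 32r/28) / [s(1 + 32r/28) + 1 − s]

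| r | Serious count multiplied by | Share if s = 10% | Share if s = 20% | Share if s = 50% |
|---|---|---|---|---|
| 0 | 1.00 | 10.0% | 20.0% | 50.0% |
| 0.1 | 1.11 | 11.0% | 21.8% | 52.7% |
| 0.25 | 1.29 | 12.5% | 24.3% | 56.2% |
| 0.5 | 1.57 | 14.9% | 28.2% | 61.1% |
| 1 | 2.14 | 19.2% | 34.9% | 68.2% |

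Worked row, s = 20% and r = 0.25: 0.2 × 1.2857 = 0.2571, and 0.2571/(0.2571 + 0.8) = 24.3%. The last row is an extreme. If each subject had one serious event by Day 28, r = 1 would mean 21 × 32/28 = 24 new serious events on Days 29 to 60, which nothing in the documents supports.

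**5. Severity.** Keep s = 20% and r = 0.25. If 80% of serious and 10% of non-serious events are graded severe, the severe share moves from 0.8 × 0.2 + 0.1 × 0.8 = 24.0% to (0.8 × 0.2571 + 0.08)/1.0571 = 27.0%. If both types are graded severe 10% of the time, it stays at 10%. So the direction depends on how late serious events are graded.

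**The case against.** The strongest reply is that the SAP follows its protocol. The protocol's own definition of a treatment-emergent event (7.2.3.1) has no upper limit either, and SAP 4.2 and 8.2 state the safety endpoint without mentioning Day 28. Serious events to Day 60 are real events and belong in the report. SAP 8.2.1 also lists all treatment-emergent events by subject and lists serious and fatal ones separately. With 21 subjects and onset dates recorded, a reader could pick out the late ones. The SAP specifies no ratio of serious to all events, so a shift in that share is a reader's inference from the tables and not a planned statistic.

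Much of this is fair, and it limits the point to a mismatch that can be repaired. It does not remove it. SAP 3.1 keeps the Day 1 to Day 28 window, SAP section 6 does not list its removal as a change, and listings do not correct a summary table whose period is unstated.

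Three stronger readings are tempting, and the documents do not support them:
- *After Day 28 only serious events are collected, giving a fixed 28/32-day split.* That follows section 3 alone. Under 6.4.1, full capture may run past Day 28 for subjects still in hospital, or stop before it for those discharged early.
- *The tables therefore overstate severity.* Seriousness (protocol 6.1.2) and severity (6.2.1) are separate scales, and step 5 shows that the severity mix need not move.
- *The arm with better survival looks worse.* Both arms have the same collection rules, and no survival or event rates are given. Such an effect is possible, but nothing here demonstrates it.

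**Conclusion.** The mismatch stands: a Day 1 to Day 28 objective is reported through tables open to Day 60, and the added period has uneven capture. This rests on the text of both documents and needs no assumed rate.

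Its size cannot be determined from the documents. It is nil if no serious event starts after Day 28. The serious count otherwise rises, and in a three-subject active cohort a single subject whose only serious event is late changes serious-event incidence by 33 points. The shares in step 4 are illustrations, not estimates. The point concerns what the tables describe; it does not show a distorted comparison between USB002 and placebo.

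**What to change.** 1. In SAP 7.2 and 8.2.1, limit the primary treatment-emergent tables to events with onset from first infusion through Day 28, and state the window in the table titles.
2. Report serious and fatal events with onset on Days 29 to 60 in a separate table and listing. Leave Day 60 all-cause mortality in SAP 8.3.1.
3. Reconcile the end of event collection between protocol section 3 and protocol 6.4.1, and record which rule the sites applied. A Day 28 cut alone does not give uniform capture if new non-serious events stopped at an earlier discharge. In that case, identify the subjects with serious-only capture before Day 28 and footnote the tables.

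The cost is one date condition in the analysis dataset, one extra table and listing, and a short clarification of the collection rule. The downside is small: late serious events leave the main table, but they are still reported in full.

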8.2.2. Respiratory Results

All respiratory data, including all assessments, Non-invasive Mechanical Ventilation (NIV) data, and Mechanical Ventilation Status (MVS) data, will be listed.

8.2.3. Laboratory Assessments

Laboratory assessments with quantitative results, including raw assessments at each visit and change from baseline at post-baseline visits, will be summarized by dose level cohort, and visit for each test.

Each no-missing lab result's normal/abnormal status (e.g., normal/low/high for quantitative results, and normal/abnormal for qualitative results) will be calculated based on the normal reference ranges provided by the lab. The status will be summarized using shift tables from baseline to each post-baseline time point.

All lab data will be presented in by-subject data listing.

8.2.4. ECG Assessments

ECG assessments (heart rate, PR interval, QRS duration, QT interval, QTcF and QTcB intervals, and overall assessments (Normal /Not clinically significant abnormal /Clinically significant abnormal) will be summarized by dose level cohort and visit.

Change of ECG values from baseline values will be summarized for all post-baseline visits.

8.2.5. Vital Signs

Vital Signs (weight, BMI, systolic and diastolic blood pressure, heart rate, and temperature) will be summarized by dose level cohort and visit.

Change of vital signs (weight, BMI, systolic and diastolic blood pressure, heart rate, and temperature) from baseline values will be summarized for all post-injection visits.

Unscheduled vital signs will only be presented in by-subject listing.

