### **3.1.4. Dosage and Administration**

A new, unused vial will be used for each dose. The total dose administered will be dispensed per kg of body weight. USB002 or placebo will be diluted (see pharmacy manual) in saline and infused continuously by a dedicated line.

Pharmacy will prepare USB002 or placebo and provide the final product for infusion to the study team in a 100 mL sodium chloride (0.9%) Injection, *USP* bag(s). USB002 or placebo should not be administered with other medications in the same IV line and require a dedicated line. The infusion of study medication (USB002/placebo) may be piggy-backed on a 0.9% saline infusion if it is being used specifically and solely for the purpose of keeping vascular access open i.e. TKVO.

If possible, no other procedures should be performed within 90 minutes of the start of infusion; procedures or medication which may induce hypotension (BP decrease by 20% mmHg systolic) should be avoided during the same period.

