### **3.2. Dose Regimen and Escalation**

#### Part 1: Dose Escalation

During dose escalation, the study will follow a traditional “3+3” design with three subjects in each cohort receiving SOC plus USB002 and three subjects in each cohort receiving SOC plus placebo. Cohorts will be enrolled sequentially for USB002 dose, with subjects receiving active drug at four sequential cohort doses of 90, 300, 600 and 900 ug/kg/day.

DSMB escalation decisions will be conducted on unblinded data. In Part 1, data review to determine dose escalation, de-escalation and study stop will be conducted by the DSMB after the last subject in each cohort has completed infusion (96-hour timepoint). Recruitment will be halted during DSMB data review for dose escalation decisions. Notification of changes in dose concentrations (escalation or de-escalation) will be issued through the IWRS.

The first 6 subjects (3 SOC plus USB002 subjects and 3 SOC plus placebo subjects) will be treated at the lowest dose. If one subject experiences an AE that is determined by the DSMB to be a potential DLT, an additional 6 subjects (3 SOC plus USB002 and 3 SOC plus placebo) will be treated at the same cohort dose. If DLTs are experienced in the new cohort at the same dose, the study may be stopped, or dose de-escalated.

DLT of hypotension (systolic BP < 90 mmHg) is a possibility, which may require the administration of fluid boluses or IV pressor agents.

At the time of a DSMB safety review, if no DLTs are identified in the first cohort, approval will be issued to treat the next 6 subjects (3 SOC plus USB002 and 3 SOC plus placebo) at the next dose. The DSMB safety reviews will be repeated between cohorts until the MTD or top dose of 900  $\mu$ g/kg/day is reached.

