### 5.3 Other Assays or Procedures

Other assays or procedures include:

- Pregnancy test (for females of childbearing potential).
- OSCI (Appendix 1);
  - In addition to study required OSCI status collection, any additional OSCI assessments conducted during the study will also be collected.
- SBT (Appendix 2);
- Chest X-ray (required at screening only);

- 12-lead ECG to include HR and QRS intervals, QT/QTcF/QTcB; Correlation of QT values using Fridericia's formula;
- Vitals to be captured daily; and during the infusion period at a minimum of every 8 hours. Vitals to include systolic and diastolic BP, HR, RR and temperature;
  - If BP changes significantly post start of infusion, mean arterial pressure will be collected at 15-minute intervals, until resolution;
- Weight measured at screening only;
- Study-required respiratory assessments (first and last assessments can be based on 24 hour clock or from infusion time):
  - Arterial Blood Gas (ABG): If multiple assessments are conducted daily, the first and last assessment of the day will be collected; missed ABGs do not qualify as deviations,
  - $\text{FiO}_2$  (%) – The highest value in a 24-hour period to be recorded in the event of multiple daily assessments,
  - $\text{PaO}_2/\text{FiO}_2$  ratio, the  $\text{PaO}_2$  value to be obtained from the ABG when performed,
  - Respiratory rate (breaths/min) – The highest value in a 24-hour period to be recorded in the event of multiple daily assessments,
  - $\text{SpO}_2$  (%) – The lowest value in a 24-hour period to be recorded in the event of multiple daily assessments.

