# 6. ASSESSMENT OF SAFETY

## 6.1. Safety Parameters

Safety assessments to be conducted in this study include:

- AEs collected at all study visits from the time of first study drug dose;
- Changes in concomitant medications;
- Findings from physical examinations;
- Changes in laboratory parameters;
- Changes in respiratory and cardiovascular assessments.

Safety and tolerability will be assessed by the DSMB (see Section 6.6).

Any AE that is considered definitely, probably, or possibly related to USB002 is potentially a DLT. DLT will be defined per the DSMB SMP.

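### SAP 8.2.5 gives no count of subjects with systolic BP below 90 mmHg and keeps unscheduled readings out of the BP tables, so a low reading between scheduled times is counted only if it is reported as an adverse event

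*SAP*

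**What the plan says.** BP is part of the primary safety objective (protocol 2.1.1; SAP 3.1). Protocol 3.2, Part 1, states: "DLT of hypotension (systolic BP < 90 mmHg) is a possibility, which may require the administration of fluid boluses or IV pressor agents". No other specific DLT is named. Protocol 6.1 adds the general route, "Any AE that is considered definitely, probably, or possibly related to USB002 is potentially a DLT", and leaves the definition to a separate plan: "DLT will be defined per the DSMB SMP".

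Protocol 5.3 calls for vital signs daily and "during the infusion period at a minimum of every 8 hours". If BP changes significantly after the infusion starts, "mean arterial pressure will be collected at 15-minute intervals, until resolution". Section 5.4.2 applies the 5.3 collection during infusion where there is no continuous monitoring of vital signs. The Part 1 schedule (Table 2) has columns after infusion start at 4, 8, 12, 24, 32, 40, 48, 72 and 96 hours.

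SAP 8.2.5 summarises weight, BMI, systolic and diastolic BP, heart rate and temperature by cohort and visit, as values and changes from baseline. MAP is not in the list. The section ends: "Unscheduled vital signs will only be presented in by-subject listing". Protocol 7.2.3.3 planned by-patient listings with notable values flagged. SAP 8.2.5 does not mention a flag, and SAP section 6 does not record dropping it.

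SAP 8.2.1 counts DLTs in the adverse event overview and in a separate summary, and lists them separately. It also tabulates all treatment-emergent events by system organ class and preferred term, by dose cohort with placebo combined.

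**The concern.** Readings taken because a subject's BP has moved are by nature off-schedule. Under SAP 8.2.5 they are left out of the BP tables, and MAP is left out altogether. What remains is a by-visit summary that can look unremarkable at a dose where a subject fell below the protocol's own threshold between visits.

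Other safety data are treated differently. Laboratory values get normal/low/high shift tables (SAP 8.2.3), and ECGs get a clinical-significance category (SAP 8.2.4). BP, which carries the one named toxicity, gets no abnormality category.

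The stake is the description of tolerability by dose. With three active subjects planned per cohort, one subject below 90 mmHg is 1/3 = 33% of that dose group, and a mean at fixed visits is a poor way to show it.

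**Working it through.** The documents state no figure on this point that could be reproduced. The check compares the planned outputs and then the two collection schedules.

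**Step 1. Where a systolic BP below 90 mmHg would show.**
- By-visit BP summary (SAP 8.2.5, statistics in 7.4): a low value at a scheduled time appears as the lower end of the range for that visit. Nothing counts subjects across visits, and an unscheduled value does not enter.
- By-subject listing (SAP 8.2.5): every reading is there, with no flag specified in the SAP.
- Adverse event and DLT tables (SAP 8.2.1): the event is counted whenever the reading was taken, provided it was reported as an adverse event. The DLT rows also need a DSMB determination (protocol 3.2).
- Concomitant medication tables (SAP 8.4.1): a recorded vasopressor appears by drug class. The separate endpoint on inotropes and vasopressors is not analysed (SAP 6.3), although SAP 4.2 and 8.2 still name those drugs within the primary safety endpoint.

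Neither document sets a numerical rule that a reading below 90 mmHg must be reported as an adverse event. A low reading between columns that is not reported, and not treated with a recorded drug, therefore reaches only the listing.

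**Step 2. Eight-hourly minimum against the schedule columns.** Inputs: protocol 5.3 (8-hourly), 3.4 (up to 96 hours), Table 2 and 5.4.2 (columns).
- Readings after infusion start: 96 / 8 = 12, at 8, 16, 24, 32, 40, 48, 56, 64, 72, 80, 88 and 96 h.
- With a column: 8, 24, 32, 40, 48, 72 and 96 h = 7.
- Without a column: 16, 56, 64, 80 and 88 h = 5, and 5/12 = 42%.
- After 48 h: 4 of 6 have no column.
- Longest gap between columns: 24 h (48 to 72 h and 72 to 96 h).

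This assumes a full 96-hour infusion, readings at the minimum frequency and no continuous monitoring.

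**Step 3. Illustration, on an assumption that is not in the documents.** Suppose one low-BP episode of length d hours starts at random between 0 and 96 − d. For d up to 4, the windows of start times that reach a column do not overlap. The 96 h column adds nothing, because only an episode starting exactly at 96 − d reaches it. With 8 columns from 4 to 72 h:

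P(episode spans a column) = 8d / (96 − d)

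- d = 1: 8/95 = 8%
- d = 2: 16/94 = 17%
- d = 4: 32/92 = 35%
- d = 8: the windows merge to starts in 0–12, 16–48 and 64–72 h, so (12 + 32 + 8)/88 = 52/88 = 59%

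These figures show how little of the infusion the columns sample for short episodes. They are not the chance that an event goes unreported.

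**The case against.** The strongest reply is that hypotension is already counted. This is right as far as it goes. A reader might infer from SAP 8.2.5 that the named toxicity is never counted; SAP 8.2.1 rules that out. It counts and lists DLTs, and its tables by class and preferred term include every treatment-emergent event whatever its attribution or time of reading. Only the unreported low reading is left.

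A reader might also take the 42% as the share of readings excluded. The documents do not support that. The 8-hourly readings are required by the protocol, so lacking a column does not make them unscheduled, and the SAP does not say how they are classed.

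Nor would a count of readings below 90 mmHg be a DLT count. The protocol calls hypotension a possibility, and the definition sits in the safety management plan, which was not available for this review.

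It can be said too that the consequence is limited. Enrolment stopped at 21 subjects, the analysis is descriptive with no inference (SAP 7.4), Part 2 is cancelled, and the DSMB reviewed all available safety data rather than these tables (protocol 6.6). At this size a reader can go through the listing. All of that stands, and it rules out a claim that the reported dose-toxicity picture is biased as a whole. It does not remove the gap: the SAP specifies no flag for that listing, and a listing gives neither a count by dose nor a comparison with combined placebo.

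Finally, protocol 3.1.4 says that, if possible, "no other procedures should be performed within 90 minutes of the start of infusion", while the first scheduled BP after infusion start is at 4 hours. It is tempting to ask for an earlier scheduled reading. But 3.1.4 concerns other procedures and drugs that may lower BP and sets no BP assessment; enrolment has ended; and the request would be a monitoring schedule, not a correction to the analysis.

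**Conclusion.** The point holds as a limited gap in the safety tables. SAP 8.2.5 has no count of subjects below the threshold in protocol 3.2, no lowest post-baseline BP and no MAP, and it confines unscheduled readings to a listing. Hypotension is counted only when it is reported as an adverse event or judged a DLT.

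Five of 12 minimum-frequency readings have no schedule column; whether they enter the by-visit tables is undetermined. How many low readings went unreported cannot be known from the documents and may be none. The conclusion rests on SAP 8.2.5 being read as written, on the absence of a stated rule that turns a reading below 90 mmHg into a reported event, and on the safety management plan not supplying such a count elsewhere. The change is worth making because it is cheap and uses the protocol's own threshold.

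**What to change.** In SAP 8.2.5, add one descriptive table by dose level with placebo combined, using all scheduled and unscheduled readings from infusion start through the 24-hour observation period. Show:
- the number of subjects with any systolic BP below 90 mmHg;
- the lowest systolic BP, and the lowest MAP where recorded;
- the largest fall in systolic BP from baseline.

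Flag readings below 90 mmHg in the by-subject listing, which also restores the intent of protocol 7.2.3.3. Label the count as a BP-threshold count, not a DLT count. State in the SAP how 8-hourly readings without a schedule column are classed.

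The cost is one extra table and a listing flag, built from BP readings that the protocol already requires. MAP needs the qualifier because neither document shows a data field for it. No change to the assessment schedule is needed.
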